4.5.3 Additional follow-up for related hepatic toxicities

Hepatic toxicity monitoring includes the following LFTs: albumin, ALT, AST, total bilirubin (fractionated if total bilirubin $> 2 \times \text{IULN}$), alkaline phosphatase (fractionated if alkaline phosphatase is grade 2 or higher) and GGT. For patients with Gilbert Syndrome: total and direct bilirubin must be monitored, intensified monitoring applies to changes in direct bilirubin only.

Close observation is recommended in case of AST, ALT, and/or bilirubin increase requiring dose interruption, which involves:

- Repeating liver enzyme and serum bilirubin tests two or three times weekly. Frequency of re-testing can decrease to once a week or less if abnormalities stabilize or return to normal values.
- Obtaining a more detailed history of current symptoms.
- Obtaining a more detailed history of prior and/or concurrent diseases.
- Obtaining a history of concomitant drug use (including non-prescription medications, herbal and dietary supplements), alcohol use, recreational drug use, and special diets.
- Ruling out acute viral hepatitis types A, B, C, D, and E; hepatotropic virus infections (CMV, EBV or HSV); autoimmune or alcoholic hepatitis; NASH; hypoxic/ischemic hepatopathy; and biliary tract disease. Hepatitis testing is not mandatory; to be done per investigator discretion.
- Obtaining a history of exposure to environmental chemical agents.
- Obtaining additional tests to evaluate liver function, as appropriate (e.g., INR, direct bilirubin).
- Considering gastroenterology or hepatology consultations.
- Assessing cardiovascular dysfunction or impaired liver oxygenation, including hypotension or right heart failure as possible etiologies for liver dysfunction.

4.5.4 Ribociclib/placebo dose adjustment and management recommendation for related non-hematological adverse reactions

Grade	Dose Adjustment and Management Recommendations
1	No dose adjustment required. Initiate appropriate medical therapy and monitor.
2	Dose interruption until recovery to grade ≤ 1 . Initiate appropriate medical therapy and monitor. Re-initiate ribociclib/placebo at the same dose. 
 • If the same toxicity recurs at grade 2, interrupt ribociclib/placebo until recovery to grade ≤ 1. Re-initiate ribociclib/placebo at the next lower dose level.
3	Dose interruption until recovery to grade ≤ 1 . Initiate appropriate medical therapy and monitor. Re-initiate ribociclib/placebo at the next lower dose level. 
 • If toxicity recurs at grade 2: temporary dose interruption until recovery to grade ≤ 1 and reduce ribociclib/placebo dose to the next lower dose level. • If toxicity recurs at grade 3, discontinue ribociclib/placebo.
4	Discontinue ribociclib/placebo and treat with appropriate medical therapy.

4.5.5 Dose modification guidance in case of QT prolongation

Grade	Dose Modification
For all grades	
 • Check the quality of the ECG • Perform analysis of serum electrolytes (K⁺, Ca⁺⁺, Phos, Mg⁺⁺). If below the lower limit of normal, interrupt ribociclib administration, correct with supplements or appropriate therapy as soon as possible, and repeat electrolytes until documented as normal • Review concomitant medication usage for the potential to inhibit CYP3A4 and/or to prolong the QT interval • Check compliance with correct dose and administration of ribociclib
1	No dose adjustment required.

QTcF 450-480 ms	
2 QTcF 481-500 ms	
Interrupt ribociclib
 
Perform a repeat ECG one hour after the first QTcF of ≥ 481 ms
 
If QTcF < 481 ms, restart ribociclib at the same dose. No dose adjustment required for the first occurrence
 
 If QTcF remains ≥ 481 ms, repeat ECG as clinically indicated until the QTcF returns to < 481 ms. Restart ribociclib at the same dose level. No dose adjustments required for first occurrence. If QTcF ≥ 481 ms recurs, ribociclib should be reduced by 1 dose level (please refer to the dosing schedule table) 
Repeat ECGs 7 days and 14 days after dose resumption (then as clinically indicated) for any patient who has therapy interrupted due to QTcF ≥ 481 ms

3 QTcF ≥ 501 ms on at least two separate ECGs	
Interrupt ribociclib/placebo
 
 Consider consulting a local cardiologist Perform a repeat ECG one hour after the first QTcF of ≥ 501 ms. If QTcF remains ≥ 501 ms, repeat ECG as clinically indicated, but at least once a day until the QTcF returns to < 481 ms. If QTcF returns to < 481 ms, ribociclib/placebo should be reduced by 1 dose level (please refer to the dosing schedule table). 
Repeat ECGs 7 days and 14 days after dose resumption for any patient who has therapy interrupted due to QTcF ≥ 501 ms
 
 If QTcF of ≥ 501 ms recurs, discontinue ribociclib/placebo
4 QT/QTcF ≥ 501 or > 60 ms change from baseline and Torsades de pointes or polymorphic ventricular tachycardia, or signs/symptoms of serious arrhythmia	
Discontinue ribociclib/placebo
 
 Obtain local cardiologist consultation Perform a repeat ECG one hour after the first QTcF of ≥ 501 ms 
If QTcF remains ≥ 501 ms, repeat ECG as clinically indicated, but at least once a day until the QTcF returns to < 501 ms.

4.5.6 Management of All Other Related Adverse Reactions:

Consider performing an analysis of serum potassium, calcium, phosphorus, and magnesium, for all adverse reactions that are potentially associated with electrolyte imbalance (e.g. diarrhea, nausea/vomiting). If the electrolyte values are below the lower limit of normal, interrupt ribociclib administration, correct electrolytes with supplements as soon as possible, and repeat electrolyte testing until documented normalization of the electrolytes.

4.6 Surgery:

4.6.1 Schedule: Surgery should be scheduled during days 8-22 of the 6th cycle of neoadjuvant endocrine therapy. Protocol therapy will be continued until the day before surgery.

Note: A surgical delay beyond the time frame described above, requires a discussion with the principal investigator or co-investigator. Given the subject population (older with co-morbid illnesses) it may be appropriate for a subject to remain on the endocrine agent to allow a delay in surgery to allow a recovery from inter-current illness for example. These issues will be dealt with on a case-by-case basis.

4.6.2 Breast surgery: The type of breast surgery (either mastectomy or lumpectomy) is determined by the treating surgeon according to institutional standard, with the goal to

completely excise the tumor. A negative margin is required unless further excision is not possible.

4.6.3 Lymph node surgery: The type of lymph node surgery (sentinel lymph node with or without axillary lymph node dissection) will be determined by the treating surgeon according to institutional standard.

4.6.4 Surgical pathology report: Size of the breast tumor; number of lymph nodes examined and the number of positive by H&E staining; final tumor margins; and extent of surgery should be reported with submission of surgical and pathology reports.

4.6.5 Required tissue sampling at surgery: Two core biopsies frozen in separate blocks and two formalin-fixed core biopsies should be obtained (preferred). Tumor samples may also be removed by dissection of the surgical specimen (not preferred) as long as the samples are frozen or fixed within 30 minutes of removal from the subject. In addition, slides for PEPI score will be collected from fixed surgical pathology tumor tissue blocks.

4.7 Postoperative chemotherapy:

PEPI 0 Group: Adjuvant chemotherapy is not recommended. However, decision regarding use of adjuvant chemotherapy will be left to the discretion of treating physician.

PEPI >0 Group: Adjuvant chemotherapy is recommended at the discretion of treating physician and will be documented by online data submission. Subject may participate in other adjuvant clinical trials.

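### Section 4.5.5: the grade 2 and grade 3 QT headings do not match their own steps, so a single unconfirmed QTcF of 501 ms or more has no clear dose action

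*Combined protocol and SAP*

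**What the plan says.** All the wording is in the QT table of section 4.5.5; the dose levels are in section 4.5.

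- **Grade 2.** The heading is "QTcF 481-500 ms". Drug is interrupted, and the next step is "Perform a repeat ECG one hour after the first QTcF of ≥ 481 ms", which has no upper limit. If the repeat is below 481 ms, the instruction is "restart ribociclib at the same dose. No dose adjustment required for the first occurrence". If a QTcF of 481 ms or more comes back, the dose goes down one level.
- **Grade 3.** The heading is "QTcF ≥ 501 ms on at least two separate ECGs". Drug is interrupted, and the confirming ECG is ordered inside the row: "Perform a repeat ECG one hour after the first QTcF of ≥ 501 ms". If the value stays at 501 ms or more, ECGs are repeated at least daily until it is below 481 ms. The next item reads "If QTcF returns to < 481 ms, ribociclib/placebo should be reduced by 1 dose level". If 501 ms or more comes back, drug is discontinued.
- **Grade 4** (with torsades, polymorphic ventricular tachycardia or signs of serious arrhythmia). Drug is discontinued, cardiology consultation is required, and ECGs continue as clinically indicated but "at least once a day until the QTcF returns to < 501 ms".

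The dose levels in section 4.5 are 600, 400 and 200 mg and then discontinuation in Arm B, and 400 and 200 mg and then discontinuation in Arm C.

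**The concern.** A table of this kind works if the headings sort every ECG result into one row and the steps in that row apply only to results sorted there. Here the headings leave a hole (one reading of 501 ms or more, not confirmed), while the first steps of the two rows overlap (any such reading triggers both). A site holding that result must choose a row, and the row may decide the dose.

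QT prolongation is listed among the main adverse reactions of ribociclib (sections 1.5 and 8.2), and the study calendar schedules an ECG on Day 1 of Cycles 2 to 6, so this is the table a site consults when one is abnormal. In a multi-center trial, two sites could follow the text in good faith and give different doses for identical ECGs. No other section settles it: the general non-hematological table in section 4.5.4 works by grade, and the grade is what is unclear.

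**Working it through.** The plan states no figure to reproduce. The check runs example ECG sequences through the headings and steps of the grade 2 and grade 3 rows. The millisecond values are illustrative assumptions. Each case is a first occurrence without signs of arrhythmia, and the last value is the return below 481 ms. The grade 3 item on return below 481 ms is read in two ways: on its own, or only after QTcF has stayed at 501 ms or more on the repeat.

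| Sequence (ms) | Heading met | Grade 2 steps | Grade 3 item, alone | Grade 3 item, in sequence |
|---|---|---|---|---|
| 490, 470 | grade 2 | same dose | not triggered | not triggered |
| 510, 470 | none | same dose | one level lower | not triggered |
| 510, 490, 470 | grade 2, by the second ECG | same dose | one level lower | not triggered |
| 510, 505, 470 | grade 3 | grade 2 heading not met | one level lower | one level lower |

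**First-event dose.** The first and last sequences are settled by their headings. In the second, no heading fits: one ECG is at 501 ms or more and none lies in 481-500 ms. In the third, the repeat falls in the grade 2 band, but a site that has started the grade 3 steps finds nothing there for a repeat of 481-500 ms.

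**Size where the readings differ.**
- Arm B: 600 versus 400 mg; (600 − 400) / 600 = 33%.
- Arm C: 400 versus 200 mg; (400 − 200) / 400 = 50%, and 200 mg is the last level before discontinuation.

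**Recurrence.** A second event at 501 ms or more is also a second event at 481 ms or more, so it meets the grade 2 wording (reduce) and the grade 3 wording (discontinue).
- Arm B at 600 mg: 400 mg or none. Arm B at 400 mg: 200 mg or none.
- Arm C at 400 mg: 200 mg or none. Arm C at 200 mg: both rules end in discontinuation, because no lower level exists.

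**End of daily ECGs.** Grade 3: below 481 ms. Grade 4: below 501 ms. The difference is 501 − 481 = 20 ms. At 481-500 ms the daily minimum has ended in grade 4 and continues in grade 3.

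**The case against.** The strongest reply is that the table confirms before it acts on the dose. A grade defined by two ECGs can be established only by taking a second one, so interrupting at the first reading and repeating an hour later is ordinary practice and no error in itself. Read in order, the grade 3 steps are: repeat; if still at 501 ms or more, keep repeating until below 481 ms; then reduce. On that reading the reduction follows a confirmed event, as the heading says, and only the grade 2 steps reach the patient with 510 then 470 ms. The extracted text does not show whether the reduction item was nested under the preceding one.

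This reply stands in part. A reader might infer that the table certainly prescribes two doses for the same ECGs. The documents do not support that, because the conflict depends on reading one item in isolation. But the item is worded as a free-standing condition, so the sequential reading is not forced either. Where it is adopted, the result still meets no heading, grade 3 still has no step for a repeat of 481-500 ms, and the recurrence rules still overlap.

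A reader might also infer that the grade 4 limit contradicts grade 3, or that follow-up is laxer after the worse event. The documents do not support that. Grade 4 stops drug permanently, so its limit cannot be a restart criterion. It ends only the daily minimum, with ECGs otherwise as clinically indicated, and cardiology consultation is required where grade 3 only suggests it. What remains is that no reason is given for the difference.

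The case is also narrow. Both rows interrupt drug at once, and the steps for all grades include a check of ECG quality, which may dispose of some isolated readings. The documents give no frequency for a QTcF of 501 ms or more. Among the 10 patients on ribociclib plus letrozole in section 1.6, neutropenia was the only grade 3 or 4 toxicity.

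**Conclusion.** The point holds as a mismatch between headings, triggers and recurrence rules in the grade 2 and grade 3 rows. It is limited to a reading of 501 ms or more that the repeat does not confirm, and to recurrences at that level. Depending on how one grade 3 item is read, the first case is either a difference of one dose level (33% in Arm B, 50% in Arm C, from the starting dose) or a gap in the headings. The recurrence overlap is between reduction and discontinuation, except in Arm C at 200 mg, where both lead to discontinuation.

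Two ECGs at 501 ms or more leave no conflict over the first-event dose. Sample size and the primary analysis are not affected. How often the situation would arise cannot be estimated from the documents. The grade 3 and grade 4 limits for daily ECGs call for confirmation only. The conclusion rests on the table as extracted; nesting lost in extraction could settle the reading of the reduction item, but not the heading gap or the recurrence overlap.

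**What to change.** Reconcile the grade 2 and grade 3 rows of section 4.5.5 so that every ECG sequence falls in one row with one dose action. Three places need attention:

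- the headings and first-step triggers, so that an unconfirmed QTcF of 501 ms or more has a row, whether the repeat is below 481 ms or in 481-500 ms;
- the grade 3 item on return below 481 ms, stating whether it requires a confirmed reading;
- the recurrence rules, so that a recurrence at 501 ms or more meets only one of them.

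Which row, dose action and recurrence rule apply is for the sponsor's clinical team to decide. As a secondary point, the sponsor should confirm that the different limits for ending daily ECGs in grades 3 and 4 are intended, and state the reason.

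The cost is rewording one table by amendment, with the usual IRB approval and notice to sites. The statistical analysis does not change.

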4.7.1 Postoperative endocrine therapy

In subjects who received adjuvant chemotherapy, adjuvant endocrine therapy is to be administered within 2-8 weeks of the completion of adjuvant chemotherapy based on evaluation of chemotherapy related toxicities.

In subjects for whom adjuvant chemotherapy is not planned, adjuvant endocrine therapy is to be administered within 2-8 weeks postoperatively.

5.0 Study Calendar: (Cycle length is 28 days)

	Screening ^A	Prior to start of study treatment	Day 14 of Cycle 1 (+7 days)	Day 1 of Cycles 2-6 (+/-3 days)	Day 1 of Cycle 3 (+/- 7 days)	EOT Days 8-22 of Cycle 6	EOT (any reason other than treatment completion)	SURGERY
Informed Consent	X							
Days 8-22 of Cycle 6
 
See section 5.1 for post-op follow-up
 
Research biopsies will be obtained at surgery (G)

Medical History/Demographics	X							
Review Eligibility Criteria	X							
Physical Exam (including vitals, height & weight)	X			X			X	
Prior & Concomitant Medications ^J	X			X			X	
Performance Status	X			X			X	
Adverse Event Assessment	X			X			X	
CBC, CMP, PT/INR	X			X		X ^I	X	
Magnesium, Phosphorus	X							
Fasting Lipid Profile	X			X ^E				
Urinalysis	X			X			X	
Measurement of breast lesions ^B	X			X			X	
Randomization		X						
Drug dispensing		X		X				
Drug compliance assessment (Participant Pill Diary Review)				X			X	
Mammogram, US of breast/axillary masses	X ^C					X	X	
MRI breast	X				X	X ^H	X	
ECG	X			X				
Echocardiogram	X ^F							
Tumor Biopsies	X ^D		X ^D			X ^G	X ^G	
Research blood samples	X ^D					X	X	

See footnotes below

- A. No more than 21 days prior to registration
- B. Using a standard cm calibrated caliper, measuring tape or ruler, the longest axis and the perpendicular axis of the tumor are to be measured and recorded in metric notation. Baseline evaluation should be done no more than 21 days prior to initiation of study therapy.
- C. Baseline mammogram, MRI and ultrasound of the diseased breast must be completed within 42 days of registration. MRI must include bi-dimensional breast tumor measurements. Mammogram of the contralateral breast is required to be within 12 months unless a mastectomy was performed. If a subject cannot have an MRI for any reason they will still be able to enroll. US and mammogram alone will then be used for tumor assessments.
- D. Pre-treatment core biopsies and research blood sample for correlative studies are required prior to the initiation of protocol therapy. Samples obtained at the time of diagnosis before registration may be submitted if they were collected according to the tissue acquisition instructions outlined in protocol (Section 9). It is advised that the baseline samples are harvested during ultrasound guided clip placement (section 9). A core biopsy will also be performed on day 14 and Ki67 will be calculated. If more than 10% of the cells express Ki67, subject will be removed from the study.
- E. Fasting Lipid Profile at Screen and Cycle 4 only.
- F. ECHO at screening and as clinically indicated throughout dose administration
- G. Required research tumor tissue biopsies will be obtained at the time of surgery. Sample submission for Ki67 and correlative studies is required (Section 9). Calculation of PEPI score is described in Section 2.4)
- H. May be obtained at the discretion of the surgeon.
- I. CBC only
- J. Concomitant medications will be reviewed at each study visit, only prohibited concomitant medications will be entered into the CRFs

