Neoadjuvant endocrine therapy with an AI such as letrozole has become a standard of care in postmenopausal women with ER+ breast cancer because of improvement in the rate of breast conserving surgery observed in previous neoadjuvant tamoxifen and aromatase inhibitor trials [Chia 2010]. In the letrozole P024 trial, 337 previously untreated ER+ and/or PR+ postmenopausal breast cancer patients were randomized between 2.5mg of letrozole or 20mg of tamoxifen daily for 4 months followed by surgery (Eiermann 2011). The clinical response rate was superior in the letrozole group (55% vs 36%, $p < 0.001$). The secondary endpoint, qualification for breast conserving surgery, was improved in the letrozole group (45% letrozole vs 25% tamoxifen, $p = 0.02$). Furthermore, the reduction in proliferation marker Ki67 was greater with letrozole over tamoxifen (87% vs 75%, $p = 0.0009$).

1.5 Study Agent (s) Background and Associated Known Toxicities:

Ribociclib is an orally bioavailable highly selective small molecule inhibitor of CDK4/6. CDK4/6 induces G1 arrest in a variety of pRb positive cancer cells, in vitro. In the mammalian cell cycle, entry into S phase is achieved by cyclin-dependent kinases 4 and 6 (CDK4/6) that activates a family of E2F transcription factors by phosphorylating and deactivating the retinoblastoma

protein (pRb). Several lines of evidence suggest that increased CDK4/6 activity contributes to tumorigenesis. Agents that inhibit the activity of CDK4/6 may be able to slow or stop the proliferation of these cancers and thereby function as effective anti-cancer drugs.

Elimination of ribociclib is dominated by oxidative metabolism mainly via CYP3A4 with a minor contribution by flavin-containing monooxygenase 3 (FMO3). The elimination of ribociclib may be affected by co-administered drugs that inhibit or induce CYP3A4.

Based on its mechanism of action, the results of the preclinical toxicology studies and available clinical safety data as of September 10, 2014, the following are identified as the main adverse reactions for ribociclib: bone marrow suppression including leukopenia, neutropenia, anemia, and thrombocytopenia, renal toxicity, fatigue, nausea, vomiting, abdominal pain, diarrhea, pneumonia and prolongation of the QT interval. The risk of these toxicities may be amplified by concomitant administration of strong inhibitors of CYP3A4 or other combination treatments.

1.6 Rationale for combining CDK4/6 inhibitor ribociclib and letrozole:

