4.0 TREATMENT

4.1 Treatment Dosage and Administration:

Arm A (Control):

Agent	Dose and Route	Day	Schedule
Letrozole	2.5 mg daily by mouth	Days 1-28	Every 4 weeks x 6 cycles
Ribociclib matching placebo (random assignment of placebo)	3 capsules daily by mouth or 2 capsules daily by mouth	Days 1-21 (21 days on, 7 days off) or Days 1-28	

Arm B (Experimental):

Agent	Dose and Route	Day	Schedule
Letrozole	2.5 mg daily by mouth	Days 1-28	Every 4 weeks x 6 cycles
Ribociclib	600 mg daily by mouth (3 capsules of 200 mg)	Days 1-21 (21 days on, 7 days off)	

Arm C (Experimental):

Agent	Dose and Route	Day	Schedule
Letrozole	2.5 mg daily by mouth	Days 1-28	Every 4 weeks x 6 cycles
Ribociclib	400 mg daily by mouth (2 capsules of 200 mg)	Days 1-28	

- Protocol treatment to begin within 14 days of randomization
- Each cycle is 28 days (+/-3 days) or 4 weeks, except cycle 6 (see below).
- Surgery must be performed between days 8-22 of cycle 6.

4.1.1 Ribociclib or Placebo must be taken as follows:

- Subjects should be instructed to take the ribociclib/placebo capsules with a large glass of water (~250mL) at the same time each day.

- Ribociclib can be taken without regard to meals; however, dietary habits around the time of dosing should be as consistent as possible throughout the study.
- Subjects should be instructed to swallow the ribociclib/placebo capsules whole and not to chew, crush or open them.
- If vomiting occurs during the course of treatment, no re-dosing of the subjects is allowed before the next scheduled dose.
- Any doses that are missed (not taken within 6 hours of the intended time) should be skipped and should not be replaced or made up on a subsequent day.
- Subjects must avoid consumption of grapefruit, Seville oranges, star fruit, pomelos, or products containing the juice of each during the entire study and preferably 7 days before the first dose of study medication, due to potential CYP3A4 interaction with the study medications. Orange juice is allowed.

4.1.2 Letrozole should be taken at the same time each day with water.

4.2 Treatment assignment and randomization:

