There will be no letrozole dose reductions. If unanticipated grade 3 or 4 toxicity is encountered, which is considered at least possibly related to letrozole, the patient will be discontinued from letrozole therapy. Missed doses of letrozole are not made up.

4.5 Dose modifications and management of toxicity for Ribociclib/Placebo:

For severe adverse reactions the following dose reduction guidelines will be used:

ARM B (Intermittent dosing arm)	Ribociclib/Placebo	
	Dose	Number of capsules
Starting dose	600 mg	3 x 200 mg capsules
First dose reduction	400 mg	2 x 200 mg capsules
Second dose reduction	200 mg	1 x 200 mg capsule
Discontinue	NA	NA

ARM C (Continuous dosing arm)	Ribociclib/Placebo	
	Dose	Number of capsules
Starting dose	400 mg	2 x 200 mg capsules
First dose reduction	200 mg	1 x 200 mg capsule
Discontinue	NA	NA

If a patient discontinues ribociclib/placebo, she will continue on study taking letrozole alone.

If a patient requires a temporary hold of study drug on Day 1 of a cycle, Day 1 will be delayed until patient restarts study drug. There is no need to repeat all procedures listed for Day 1 in Section 5.0.

4.5.1 Ribociclib/Placebo dose adjustment and management recommendation for related hematological adverse reactions:

Toxicity/Grade	Dose Adjustment and Management Recommendations
Thrombocytopenia	
Grade 1 ($\geq 75,000$ /uL)	No dose adjustment required.
Grade 2 (50,000/uL - < 75,000/uL)	Dose interruption until recovery to $\geq 75,000$ /uL. Re-initiate ribociclib/placebo at the same dose.
Grade 3 (25,000/uL - < 50,000/uL)	Dose interruption until recovery to grade $\geq 75,000$ /uL. Re-initiate ribociclib/placebo at the same dose level. If toxicity recurs at grade 3: temporary dose interruption until recovery to $\geq 75,000$ /uL and reduce ribociclib/placebo to the next lower dose level.
Grade 4 (< 25,000/uL)	Dose interruption until recovery to $\geq 75,000$ /uL. Re-initiate ribociclib/placebo at the next lower dose level. If toxicity recurs at grade 4: discontinue ribociclib.
Absolute neutrophil count (ANC)	
Grade 1 ($\geq 1,500$ /uL)	No dose adjustment required.
Grade 2 (1,000 - < 1,500/uL)	No dose adjustment required.
Grade 3 (500 - < 1,000/uL)	Dose interruption until recovery to > 1,000/uL. Re-initiate ribociclib/placebo at the same dose level. If toxicity recurs at grade 3: temporary dose interruption until recovery to > 1,000/uL and reduce ribociclib/placebo dose to the next lower dose level.

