6.1.15 Tumor assessment

- Using a standard cm calibrated caliper, measuring tape or ruler, the longest axis and the perpendicular axis of the tumor are to be measured and recorded in metric notation. Baseline evaluation should be done no more than 21 days prior to initiation of study therapy.
- Baseline mammogram, MRI and ultrasound of the diseased breast must be completed within 42 days of registration. MRI must include bi-dimensional breast tumor measurements. Mammogram of the contralateral breast is required to be within 12 months unless a mastectomy was performed.

6.1.16 Other: ECG, Echocardiogram.

6.2 Day 14 (+7 days) of Cycle 1 (28 day cycle): Tumor Biopsies for research and calculation of Ki67.

6.3 Day 1 (+/-7 days) of Cycle 3 (28 day cycle): MRI of the breast for response assessment.

6.4 Days 1 (+/-3 days) of Cycle 2-6 (28 day cycle):

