carcinomas of the esophagus, breast, lung and pancreas. Regardless of the various genetic aberrations that may be present in the cancer cells, the anti-tumor activity of ribociclib requires the presence of functional pRb. Refer to Ribociclib (LEE011) Investigators Brochure for more details.

- Preclinical data with ribociclib in a primary model of ER+ breast cancer demonstrated synergy when given in combination with letrozole, showing complete and sustained inhibition of tumor growth (Figure below).

Figure: Ribociclib in combination with letrozole in an ER+ primary breast cancer model

Mean tumor volumes in mice treated at clinically relevant doses for 56 days with ribociclib (75 mg/kg qd) alone; letrozole (2.5 mg/kg qd) alone; ribociclib (75 mg/kg qd) plus letrozole (2.5 mg/kg qd); or vehicle. The combination arm shows complete inhibition of tumor growth that was sustained for more than 30 days of post-treatment observation.

Nonclinical pharmacokinetics and metabolism:

The pharmacokinetics (PK) of ribociclib was investigated in mouse, rat, dog and monkey. The absorption of ribociclib after oral administration was moderate for rats (48-84%). Oral bioavailability (BA) ranged between 10% and 65% across animal species. Time to maximum plasma drug concentration (T_{max}) was between 2 and 4 hours. Terminal half-life (T_{1/2}) of ribociclib was moderate in rodents and monkeys (~2-5 hours), and was longer in dogs (18 hours). Ribociclib is moderately bound to plasma proteins in all animal species with unbound fractions in plasma (f_u) ranging from 20-34% (human f_u = 30%). [3H]Ribociclib and metabolites were extensively distributed to tissues in male rats, but there was no uptake into the brain. *In vitro* metabolism studies showed that oxidative metabolism of ribociclib is dominated by CYP3A4 with a minor contribution of about 20% by flavin-containing monooxygenase 3 (FMO3). In rat ADME studies, ribociclib was predominantly excreted in the bile as metabolites, with limited excretion of unchanged drug in urine. The bulk of the administered dose (87%) was excreted within 24 hours. LEQ803 (N-demethylation) is a prominent metabolite in rat, monkey, and human hepatocytes, and the only metabolite in dog hepatocytes. LEQ803 is weakly pharmacologically active; however, it interacts with hERG channels *in vitro*.

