Day 16				
Day 17				
Day 18				
Day 19				
Day 20				
Day 21				
Day 22		DO NOT TAKE Ribociclib/Placebo		
Day 23		DO NOT TAKE Ribociclib/Placebo		
Day 24		DO NOT TAKE Ribociclib/Placebo		
Day 25		DO NOT TAKE Ribociclib/Placebo		
Day 26		DO NOT TAKE Ribociclib/Placebo		
Day 27		DO NOT TAKE Ribociclib/Placebo		
Day 28		DO NOT TAKE Ribociclib/Placebo

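### No scheduled ECG in Arm B follows sustained ribociclib dosing: all five post-baseline ECGs fall on Day 1 of Cycles 2-6, after the off week

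*Combined protocol and SAP*

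**What the plan says.** The ECG row of the Section 5.0 calendar is marked at screening and in the column headed "Day 1 of Cycles 2-6 (+/-3 days". It is blank for Cycle 1 Day 14, the Cycle 3 MRI visit and both end-of-treatment columns. Section 6 adds no routine ECG: 6.1.16 covers screening, and 6.4 to 6.6 list none, so the Day 1 ECGs rest on the calendar alone. The mid-cycle visit in Section 6.2 is for tissue only: "Day 14 (+7 days) of Cycle 1 (28 day cycle): Tumor Biopsies for research and calculation of Ki67".

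Section 4.1 gives Arm B 600 mg on "Days 1-21 (21 days on, 7 days off", and the intermittent-dosing diary in Appendix F prints "DO NOT TAKE Ribociclib/Placebo" against days 22-28. Arm C takes 400 mg on days 1-28. If drug is held at the start of a cycle, "Day 1 will be delayed until patient restarts study drug" (Section 4.5). No section says whether the ECG comes before or after that day's dose.

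Section 4.5.5 acts on QTcF from 481 ms and again from 501 ms. Its instruction "Repeat ECGs 7 days and 14 days after dose resumption" applies only to a woman whose drug has already been interrupted for such a reading.

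**The concern.** Section 1.5 ends its list of ribociclib's main adverse reactions with "pneumonia and prolongation of the QT interval". Section 8.2 adds a mechanistic reason for care: "LEQ803 is weakly pharmacologically active; however, it interacts with hERG channels" in vitro. The dose rules in 4.5.5 protect a patient only if an ECG is taken while QTcF is raised.

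In Arm B, which has the higher daily dose, routine readings come when drug has just been withheld for about a week. Prolongation that develops during days 1-21 and settles by Day 1 would not trigger the rules. Unremarkable Day 1 readings in Arm B would then say little about QTcF on 600 mg. No arm has a scheduled reading on treatment before about day 29 (day 26 at the early edge of the window).

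**Working it through.** There is no stated figure to reproduce, so the check is a count of days.

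**Inputs.** Dosing days 1-21 (Arm B) and 1-28 (Arm C), Section 4.1. ECG on Day 1 of Cycles 2, 3, 4, 5 and 6, within 3 days either way, Section 5.0. That is 5 ECGs per woman. With 40 women planned in Arm B, it is at most 40 x 5 = 200 readings.

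**Method.** Count from Day 1 of the preceding cycle, so nominal Day 1 of the next cycle is day 29 and the window runs from day 26 to day 32. Drug is dispensed at the Day 1 visit, so at a late visit the restart may have waited for it or may have happened on day 29. Both cases are shown.

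| Arm and visit | Drug-free days just before the ECG | Dosing since the last gap |
|---|---|---|
| B, 3 days early (day 26) | days 22-25 = 4 | none new |
| B, nominal (day 29) | days 22-28 = 7 | none, or 1 dose if taken first |
| B, 3 days late, restart at visit (day 32) | days 22-31 = 10 | none, or 1 dose if taken first |
| B, 3 days late, restart on day 29 | 0 | days 29-31 = 3 doses, 4 with the visit day's dose |
| C, 3 days early | 0 | at least 25 days |
| C, nominal | 0 | at least 28 days |
| C, 3 days late | 0, or 3 if the restart waits for the visit | at least 31 days, or a 28-day run ending 3 days before |

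Time since Arm B's last dose of the previous cycle is 29 - 21 = 8 days at the nominal visit and 26 - 21 = 5 days at the early edge. Scheduled Arm B ECGs on days 8-21 of any cycle: 0 of 5. An ECG at the Day 14 (+7) visit would fall on days 14-21, after about 14 to 21 consecutive doses, and these are dosing days in both schedules.

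**How much drug might remain.** The documents give no human half-life, so this is an assumed range using simple exponential decay, fraction = 0.5^(hours / half-life). Section 8.2 gives 18 h in dogs, the longest animal value. The values 48 h and 72 h are assumptions.

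| Assumed half-life | After 5 days (120 h) | After 8 days (192 h) |
|---|---|---|
| 18 h | 1% | 0.06% |
| 48 h | 18% | 6% |
| 72 h | 31% | 16% |

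Across this range the reading is taken at well below on-drug exposure, before any new dose. The documents do not say how QTcF follows concentration, so the table does not measure a lost QT signal.

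**What the documents say about frequency.** Section 8.2 lists adverse events seen in at least 10% of 10 patients on 600 mg, 3 weeks on and 1 week off, with letrozole. One patient is 10%, so the list should show every reported event, and QT prolongation is not on it. For 0 of 10, the one-sided 95% upper bound is 1 - 0.05^(1/10) = 0.259, about 26%.

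**The case against.** The strongest case on the other side is that the gap may matter little.

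- No QT event is listed among the 10 patients on Arm B's regimen (Section 8.2), and neutropenia was their only grade 3 or 4 toxicity (Section 1.6). None of the 5 dose-limiting events in 18 continuously dosed patients was a QT event. This stands as weak reassurance: the upper bound is about 26%, and the ECG timing in those patients is not given.
- Entry criteria exclude QTcF above 450 ms or unreadable, long QT syndrome, recent arrhythmia and bradycardia (3.2.19, 3.2.20). Appendix B bars drugs of known QT risk and strong CYP3A inhibitors.
- Safeguards continue on treatment. The metabolic panel, with potassium and calcium, is repeated on Day 1 of Cycles 2-6, alongside adverse event and co-medication review, and Section 4.5.6 calls for interruption when electrolytes tested because of a relevant adverse reaction are low. A reader might infer that electrolytes are checked only at entry. That is wrong, although magnesium is scheduled only at screening. None of these steps measures QTcF on drug.
- QTcF is not an endpoint, and no QTcF comparison between the two ribociclib schedules is planned. This stands: the issue is patient monitoring, with no effect on any planned efficacy analysis.
- Section 16.2 says accrual was almost complete when the first 60 women had PEPI data. A change confined to Cycle 1 would reach few women, so the fix has to cover later cycles too.

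A reader might also infer that Arm B women are always drug-free at their ECG. The documents do not support that: Day 1 is a dosing day, the order of dose and ECG is not fixed, and a late visit could follow up to 4 doses. They do support the narrower statement that no scheduled reading follows sustained dosing.

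**Conclusion.** The point holds as a monitoring gap that is cheap to close. Arm B has 0 of 5 scheduled post-baseline ECGs after sustained 600 mg dosing, while in Arm C all five follow roughly four weeks or more of dosing. The Section 4.5.5 thresholds could therefore miss on-drug prolongation in Arm B that resolves in the off week.

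This rests on the dosing and visit schedules as written, with no unscheduled dose holds. It does not depend on the assumed half-lives. How often a reading would be missed is unknown, and no count is claimed. A reader might conclude that QT events are being missed or that Arm B is unsafe. The documents give no rate of QTcF at or above 481 ms, no human half-life and no exposure-QTcF relation, so they do not support either conclusion. The wide spread in steady-state peak levels at 600 mg (859 to 5860 ng/mL, Section 8.2) does not change this, because no section ties it to QTcF.

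**What to change.** Move ECGs without adding any, and do so in all arms to keep the blind.

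1. For women who have not yet reached it, take an ECG at the existing Cycle 1 Day 14 (+7) visit, read under Section 4.5.5, in place of one later Day 1 ECG, for example Cycle 5.
2. For women past that visit, move a remaining Day 1 ECG to days 8-21 of a cycle at an existing contact. The Cycle 6 end-of-treatment visit (days 8-22) serves if the woman is still taking study drug.
3. Where no ECG is left to move, state with any QTcF results that Arm B's scheduled ECGs were taken after the off week.
4. Amend the Section 5.0 calendar and the lists in Sections 6.2, 6.4 and 6.5 to match.

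The count stays at 5 - 1 + 1 = 5 per woman, and Arm B goes from 0 to 1 reading after sustained dosing. The cost is a protocol amendment, a short test with QTcF review at a visit that now has none, and one fewer Day 1 reading per woman. In Arm C the Day 1 reading given up was itself on drug. Dropping Cycle 5 leaves 2 x 28 = 56 days between the Cycle 4 and Cycle 6 ECGs. Adding the test without removing one would mean up to 1 x 120 = 120 extra ECGs and is not proposed.
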